## 9.1 Pharmacokinetics

Pharmacokinetic variables will be analyzed for all subjects in the PK-PPS. Bimekizumab plasma concentrations will be summarized for each treatment sequence as described in Section 9, at each scheduled visit. A separate summary table will be created for the Open-Label Extension Period for subjects that are both in the PK-PPS and the OLS.

PK summaries will be based on observed values. No imputation will be used however, if plasma concentration measurements are below the level of quantification (BLQ), then for calculation of the derived statistics the result will be set to 0.125 µg/ml, which is ½ of the lower level of quantification (LLOQ). Descriptive statistics including geometric mean, geometric coefficient of variation, and geometric mean 95% CI if applicable will be calculated if at least 2/3 of the values of interest are above the LLOQ. If this is not the case, only median, minimum, and maximum will be presented. In cases where  $n < 3$  only the minimum and maximum will be presented.

In addition, geometric mean plasma concentration (with the 95% CI) will be plotted versus time on linear and semi-logarithmic scales by treatment sequence group. The summary table and figures will be repeated by cumulative antibody status for subjects randomized to bimekizumab.

If a dose is +/- 21 days out of window, then the plasma concentration from that visit and all subsequent visits will be excluded from the PK summary tables and graphs.

If the PK sampling date is >1 day after the dosing date, the plasma concentration at this visit will be excluded from the PK summary tables and figures, but not from the listing.

If a subject misses an administration of bimekizumab, receives less or more than the intended dose, then the plasma concentration from the next scheduled visit will be excluded from PK summary tables and graphs.

All PK concentration data will be listed.

## 9.2 Pharmacodynamics

Not applicable.

## 9.3 Immunogenicity

The analysis of immunogenicity for the Week 48 Interim will be based on the SS All other analyses will be based on the BKZ Set.

### 9.3.1 Anti-nuclear antibodies

Not applicable.

### 9.3.2 Anti-bimekizumab antibodies

Anti-bimekizumab antibodies will be measured using a three tiered assay approach: screening assay, confirmatory assay and titration assay. Samples confirmed as positive within the confirmatory assay, will be further evaluated in a neutralizing assay to evaluate the potential of the ADAb to neutralize the activity of Bimekizumab (IL17A or IL17F, or both) in-vitro. Samples were taken at baseline, week 1, week 2, week 4, week 8, week 12, week 16, week 20, week 24, week 36, week 48, Week 72, Week 96, Week 120, Week144 (or PEOT) and at SFU which is 20 weeks after the last dose. Due to the planned entry of some subjects to the OLE2 period, not all subjects will have an SFU period immediately following Week 144 with PK and immunogenicity samples.

Anti-bimekizumab antibody samples are not analyzed when subjects are on a treatment other than bimekizumab. For subjects who switch from secukinumab to bimekizumab, samples are analyzed starting at the visit when the switch to bimekizumab occurs. The sample at the visit when the switch occurs will act as the Baseline for that treatment group.

Screening, confirmatory and titer cut points of the respective assays will be determined by the bioanalytical laboratory based either on using commercially available drug-naïve samples or on the pre-dose samples of the study itself. The samples (or a subset) will also be subject to a neutralizing assay to evaluate whether the anti-bimekizumab antibody neutralizes the activity of bimekizumab (IL17 A or IL17F or both) in- vitro.

The following definitions will be applied regarding ADAb status of each test samples:

- An ADAb status will be confirmed as positive for any sample with an ADAb level that is positive screen and positive immunodepletion.
- An ADAb status of negative will be concluded for any sample with an ADAb level that is either negative screen or (positive screen and negative immunodepletion).

If the titer for an ADAb level that is positive screen and positive immunodepletion is missing, then a conservative approach will be used and ADAb status will be considered as positive. No imputation rules apply for the missing titer. If the ADAb level is positive screen but no confirmatory result could be determined, then a conservative approach will be used and ADAb status will be considered as positive.

Anomalous values will be not included in summaries/analysis and will be reviewed and flagged by pharmacokinetic expert.

For each subject an overall ADAb status in the treatment and OLE periods (Baseline to Week 144) will be derived:

- Overall Positive is defined as having at least one value that is confirmed positive during the treatment period.

- Overall Negative is defined as having no values that are confirmed positive at any time up to Week 144 and at least 2/3 of the protocol scheduled post-baseline assessments up to Week 144 are evaluable (i.e. neither missing as per schedule nor inconclusive)
- Overall Missing is defined as having no values that are confirmed positive at any visit in the treatment period, but the subject has 1/3 or more protocol scheduled post-baseline assessments missing (or inconclusive) up to Week 144.

This differs from the Week 48 interim analysis where all subjects were defined as either overall positive or overall negative only (a missing category was not considered). As the time on treatment is protracted in this open label extension study (up to 144 Weeks), missing data or subject discontinuation may be more prevalent and is therefore considered for the final analysis.

- The double-blind and OLE treatment periods do not include Baseline/pre-treatment samples or SFU.

Furthermore, the following subcategories for each subject will be derived:

1. **Pre anti-bimekizumab antibody negative – treatment emergent anti-bimekizumab antibody negative:** Includes subjects who are negative at Baseline and antibody negative at all sampling points post treatment (excluding SFU)
2. **Pre anti-bimekizumab antibody negative – treatment emergent anti-bimekizumab antibody positive:** Includes subjects who are negative at Baseline and antibody positive at any sampling point post treatment (excluding SFU). This group also includes subjects who have a missing pre-treatment sample (either missing or insufficient volume) at Baseline with one or more anti-bimekizumab antibody positive post-treatment samples.
3. **Pre anti-bimekizumab antibody positive – treatment emergent reduced anti-bimekizumab antibody:** Includes subjects who are positive at Baseline, and antibody negative at all sampling points post treatment (excluding SFU).
4. **Pre anti-bimekizumab antibody positive – treatment emergent unaffected anti-bimekizumab antibody positive:** Includes subjects who are positive at Baseline and are positive at any sampling point post treatment (excluding SFU) with titer values of the same magnitude as Baseline (ie, less than a 2.07 fold difference from the Baseline value).
5. **Pre anti-bimekizumab antibody positive – treatment emergent anti-bimekizumab antibody boosted positive:** Includes subjects who are positive at Baseline and are positive at any sampling point post treatment (excluding SFU) with increased titer values compared to baseline (greater than a 2.07 fold difference increase from Baseline value which will be defined within the validation of the assay).
6. **Inconclusive:** Includes subjects who have a positive pre-treatment sample and some post-treatment samples are missing, while other post-treatment samples are anti-bimekizumab antibody negative.
7. **Total treatment-emergent ADAb positivity (Category 7 [Categories 2 and 5 combined]):** Includes study participants who are pre ADAb negative – treatment-

emergent ADAb positive (Category 2) and pre ADAb positive – treatment boosted ADAb positive (Category 5).

8. **Total prevalence of pre- ADAb positivity (Category 8** [Categories 3, 4 and 5 combined]): Study participants that are tested ADAb positive at Baseline.
9. **Missing:** Includes subjects who are antibody negative at baseline, are not positive at any post-baseline visit, and have at least one missing post-treatment scheduled assessment. Note this is also applicable to subjects who have missing baseline.

For the Week 144 analysis, when all OLE and SFU data will be available, data from the OLE and SFU visits will be considered. That is, each instance of “excluding SFU” in the categories above, should be changed to “including SFU.”

In the case that a sample is collected one or more days following the scheduled visit date in which the drug was administered, the anti-bimekizumab antibody results for that sample will be associated with the scheduled visit and summarized accordingly. Such samples will also be considered when anti-bimekizumab antibody results are summarized over a given study period.

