#### Analysis

- Immunogenicity will be assessed through summary tables, figures, and listing of individual results by subject. The analysis of immunogenicity will be summarized by treatment sequence as described in Section 9 and visit. All analyses will be run on the safety population, unless specified otherwise. Summary of anti-bimekizumab antibody status overall and by each visit separated by treatment sequence
- Summary of the time-point of the first occurrence of anti-bimekizumab antibody positivity during the treatment period by treatment sequence. A plot of the titer by time to first anti-bimekizumab antibody positivity will be prepared
- All individual subject-level anti-bimekizumab antibody results will be listed.
- The number and percentage of subjects in each of the 8 anti-bimekizumab antibody categories during the treatment period by treatment sequence, with an additional category combining subjects in categories 2 and 5, summarized as total treatment emergent. In addition, the count and percentage of subjects who are pre anti-bimekizumab positive will be calculated (this is the sum of categories 3, 4, and 5)
- The prevalence of immunogenicity, separated by treatment sequence, and defined subcategory, will be reported by visit, defined as (cumulative) proportion of subjects having confirmed positive anti-bimekizumab antibody samples at any visit up to and including that visit. Missing samples will not be included in the denominator
- The time to achieving treatment-emergent anti-bimekizumab antibody positivity, separated by treatment sequence and defined sub-category, will be analyzed based on Kaplan-Meier methods. Subjects will be considered to have an event at the time point at which treatment emergent anti-bimekizumab antibody positive is first achieved. Subjects classified as treatment-emergent anti-bimekizumab antibody negative will be censored at the time of the last available anti-bimekizumab antibody result

- A summary of PASI 100 responders, separated by treatment sequence and defined sub-category, at weeks 16, 48 and 144 as a function of ADA b titer will be presented graphically. This will be repeated for PASI 75 and 90 responders

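### SAP 9.3.2: antibody categories 4 (unaffected) and 5 (boosted) can both apply to one subject, no precedence is stated, and the Baseline-positive total built on them does not match its own definition

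*SAP*

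**What the plan says.** Section 9.3.2 derives a set of antibody subcategories for each subject. For subjects positive at Baseline:

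- **Category 3 (reduced)** requires a negative result at every post-treatment sample.
- **Category 4 (unaffected)** takes subjects "positive at any sampling point post treatment (excluding SFU) with titer values of the same magnitude as Baseline", explained as "less than a 2.07 fold difference from the Baseline value".
- **Category 5 (boosted)** takes subjects "positive at any sampling point post treatment (excluding SFU) with increased titer values compared to baseline", explained as "greater than a 2.07 fold difference increase from Baseline value".
- **Category 6 (inconclusive)**: "Includes subjects who have a positive pre-treatment sample and some post-treatment samples are missing", the samples that are available being negative.
- **Category 7** combines categories 2 and 5 as total treatment-emergent positivity.
- **Category 8** is labelled as categories 3, 4 and 5 combined and described as "Study participants that are tested ADAb positive at Baseline".

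Under the Analysis heading of the same section, the count of Baseline-positive subjects is specified: "this is the sum of categories 3, 4, and 5".

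For the Week 144 analysis, the SFU sample is added to every category rule.

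**The concern.** Categories 4 and 5 each rest on what some post-treatment sample shows, and the two conditions can be met by different samples. A subject whose titer is close to Baseline at one visit and well above it at another satisfies both. The SAP gives no order between the two, does not say that the peak titer decides, and does not say that the categories exclude one another.

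At stake are the category table, the Baseline-positive total and possibly the total treatment-emergent figure. The Kaplan-Meier displays and the PASI responder displays are also split by subcategory, and the individual plots are grouped by it. Grouping works only if each subject has one category.

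**Working it through.** The SAP states no figure to reproduce. The check is one of logic, followed by a test of whether the size can be pinned down.

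**1. Can both rules be met?** Section 9.3.2 lists post-Baseline samples at Weeks 1, 2, 4, 8, 12, 16, 20, 24, 36 and 48 (10), then Weeks 72, 96, 120 and 144 (4 more, 14 in all), plus SFU. Subjects who switch from secukinumab at Week 48 take the switch visit as Baseline and have the last 4. With two or more samples, having at least one within 2.07-fold and at least one boosted are not mutually exclusive. Category 3 is disjoint from both because it demands negativity throughout. The neutralizing-antibody classes in the same section are also made exclusive, by requiring no positive sample on the other assay. Categories 4 and 5 carry no such clause.

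**2. How large is the overlap?** The SAP gives no titer distribution, so two assumed models were tried.

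(a) Independent visits. Let k be the number of samples, b the chance per sample of a boosted titer, and s the chance per sample of a positive titer within 2.07-fold:

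P(4 | 5) = [1 − (1−b)^k − (1−s)^k + (1−b−s)^k] / [1 − (1−b)^k]

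With k = 14, b = 0.20, s = 0.30: (1 − 0.0440 − 0.0068 + 0.0001) / (1 − 0.0440) = 0.993.

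With k = 4, b = 0.20, s = 0.05: (1 − 0.4096 − 0.8145 + 0.3164) / (1 − 0.4096) = 0.156.

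(b) A boost that persists once it starts (simulated, exponential onset), 14 samples:

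| Share of pre-boost samples that are negative | Mean onset 4 wk | 12 wk | 40 wk |
|---|---|---|---|
| 0% | 0.78 | 0.92 | 0.97 |
| 50% | 0.60 | 0.81 | 0.93 |
| 90% | 0.18 | 0.32 | 0.50 |
| 100% | 0 | 0 | 0 |

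For switchers with 4 samples, model (b) gives 0 to 0.50. The share of boosted subjects who also meet category 4 therefore runs from 0 to about 1, depending wholly on assumptions.

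**3. What happens to the sum?** Invented illustration with 26 Baseline-positive subjects: 5 in category 3, 6 in category 4 only, 8 in both 4 and 5, 1 in category 5 only, 4 in category 6, and 2 whose positive samples all fell more than 2.07-fold (fitting neither 4 nor 5).

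- Literal sum: 5 + (6 + 8) + (8 + 1) = 28.
- Distinct subjects in 3, 4 or 5: 5 + 6 + 8 + 1 = 20.
- Positive at Baseline: 20 + 4 + 2 = 26.

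The literal sum differs from the truth by overlap minus omitted: 8 − 6 = +2. Keeping the 9 boosted subjects but letting 4 overlap gives 4 − 6 = −2 (sum 24). With no overlap it is 0 − 6 = −6 (sum 20). The sign is not fixed.

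**4. What happens to category 7?** On the literal reading, nothing: every boosted subject still meets category 5. If each subject gets one category, the 8 mixed subjects in the illustration make the category 5 contribution either 9 or 1, according to a choice that the SAP leaves open.

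**The case against.** The strongest reply is that one category per subject is plainly meant. The subcategories are derived subject by subject, the labels unaffected and boosted are opposites, plots are grouped by category, and adding 3, 4 and 5 to count persons makes sense only if the three are disjoint. The wording can even be parsed so that the phrase about sampling points governs positivity alone, while the titer condition describes the subject's titers as a whole. A sensible programmer would put a mixed subject in category 5.

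That is a fair account of the likely intent, and it means that double counting is not certain. It does not supply the missing rule: on a one-category reading, category 7 depends on which category is chosen. The same section also refers to 8 categories for the table and 7 for the plots while listing 9, so the scheme has not been reconciled.

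Two further points against the concern stand in full. The efficacy subgroups and the adverse-event groups by antibody status have their own definitions in Section 9.3.2 and do not use categories 4 and 5. No hypothesis test depends on them either.

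**Conclusion.** The definitions of categories 4 and 5 overlap and no precedence is given. That follows from the text alone. The summed Baseline-positive count also fails to match the verbal definition of category 8, because it can count mixed subjects twice and it leaves out Baseline-positive subjects in category 6. The effect is confined to descriptive immunogenicity outputs, and the number of subjects cannot be derived from the document.

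Three stronger conclusions might be inferred and are not supported:

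- **That nearly all boosted subjects overlap.** This needs titer paths that the SAP does not give. The assumed models span 0 to about 1, and the 14-sample schedule does not apply to switchers.
- **That the Baseline-positive count is too high by the number boosted.** The double count equals only those meeting both rules, and the omitted subjects pull the other way.
- **That the boosted count or category 7 is wrong as the text stands.** On the literal reading both are intact. Category 7 is at risk only if mixed subjects are assigned to category 4.

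**What to change.** In Section 9.3.2:

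1. State that category 5 applies whenever any post-treatment titer is more than 2.07-fold above Baseline, and that category 4 requires at least one positive post-treatment sample and no such titer.
2. State explicitly where subjects belong whose samples stay positive but whose titers fell more than 2.07-fold. They now fit neither category, and step 1 alone would move them into the unaffected class without saying so.
3. Count category 8 directly from Baseline status, not as the sum of 3, 4 and 5. Precedence alone does not repair that sum: in the illustration it would give 20 against 26.

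The cost is a few clauses in one section and a rerun of the category table and the displays split by subcategory. No new data are needed.

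### Category 8 is described as Baseline ADAb positivity but is computed as Categories 3+4+5, which leaves out Baseline-positive subjects in Category 6 and any who fit no category

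*SAP*

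**What the plan says.** SAP section 9.3.2 sorts subjects into antibody subcategories. Four of them apply to individual subjects who are positive before treatment:

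- **Category 3 (reduced):** "Includes subjects who are positive at Baseline, and antibody negative at all sampling points post treatment (excluding SFU".
- **Category 4 (unaffected):** positive at Baseline and at some point after treatment, "with titer values of the same magnitude as Baseline (ie, less than a 2.07 fold difference from the Baseline value".
- **Category 5 (boosted):** positive at Baseline and at some point after treatment, "with increased titer values compared to baseline (greater than a 2.07 fold difference increase from Baseline value".
- **Category 6 (Inconclusive):** "Includes subjects who have a positive pre-treatment sample and some post-treatment samples are missing, while other post-treatment samples are anti-bimekizumab antibody negative".

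Category 8, the total prevalence of pre-existing positivity, is then given as "Categories 3, 4 and 5 combined]): Study participants that are tested ADAb positive at Baseline". The Analysis part of the section repeats the arithmetic for the number and percentage of subjects "who are pre anti-bimekizumab positive will be calculated (this is the sum of categories 3, 4, and 5".

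Two other statements in section 9.3.2 matter here. At the Week 144 analysis the category definitions are changed to include the safety follow-up (SFU) sample. The section also warns that "not all subjects will have an SFU period immediately following Week 144 with PK and immunogenicity samples".

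**The concern.** The description of Category 8 and its formula name different groups. Whether a subject was positive at Baseline is known from the Baseline sample alone. The formula makes it depend on what happened to later samples: one missing result can move a Baseline-positive subject from Category 3, which is counted, to Category 6, which is not.

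At stake is the reported prevalence of pre-existing antibodies. It can be too low. It can also differ between treatment sequences or data cuts because follow-up differs, when Baseline status does not. A programmer has to choose between the words and the sum, and the sum appears twice.

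**Working it through.** The SAP states no prevalence figure, so there is nothing to reproduce. The check is one of logic, followed by an illustration of size.

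**Step 1: can a Category 6 subject also be in 3, 4 or 5?** Category 3 needs a negative result at every post-treatment sampling point, which a subject with missing samples does not have. Categories 4 and 5 need a positive post-treatment sample, whereas in Category 6 every observed post-treatment sample is negative. So there is no overlap, and no text in section 9.3.2 adds Category 6 back or limits Category 8 to subjects with conclusive follow-up.

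**Step 2: enumeration.** Take a Baseline-positive subject with three post-treatment samples, each negative, positive at the same titer, positive and boosted, or missing. That gives 4^3 = 64 patterns, with any boosted sample assigned to Category 5:

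| Category | Patterns | In the 3+4+5 sum? |
|---|---|---|
| 3 | 1 | yes |
| 4 | 19 | yes |
| 5 | 37 | yes |
| 6 | 6 | no |
| none (all missing) | 1 | no |

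The sum captures 1 + 19 + 37 = 57 of the 64 patterns and drops 7, all of them Baseline positive. These are counts of logical patterns and carry no weight for how common each is. They show that the error runs in one direction only.

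**Step 3: falling titers.** A titer fall was not part of the enumeration. If Category 4 means within 2.07-fold in either direction, a subject who stays positive only at titers more than 2.07-fold below Baseline is not in 3 (a positive sample exists), 4 (the difference is too large), 5 (no increase) or 6 (the observed samples are not all negative).

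**Step 4: illustration of size.** Let m be an assumed, independent probability that any one sample is missing, and k the number of scheduled post-baseline samples. For a Baseline-positive subject whose observed samples are all negative, and ignoring the negligible all-missing term:

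P(Category 6) = 1 − (1 − m)^k

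Section 9.3.2 lists samples at Weeks 1, 2, 4, 8, 12, 16, 20, 24, 36, 48, 72, 96, 120 and 144, so k = 14 for subjects on bimekizumab from the start. For subjects switched from secukinumab, the sample at the switch is the Baseline, leaving Weeks 72, 96, 120 and 144, so k = 4.

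| m (assumed) | k = 14 | k = 4 |
|---|---|---|
| 1% | 1 − 0.99^14 = 13.1% | 1 − 0.99^4 = 3.9% |
| 2% | 1 − 0.98^14 = 24.6% | 1 − 0.98^4 = 7.8% |
| 5% | 1 − 0.95^14 = 51.2% | 1 − 0.95^4 = 18.5% |

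**Step 5: effect on the prevalence itself.** Suppose, purely as an example, that true Baseline prevalence is 10% and half of those subjects are negative in every observed sample. Category 8 then reports 10% × (1 − 0.5 × P):

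- k = 14: 10% × (1 − 0.5 × 0.131) = 9.3% at m = 1%, and 10% × (1 − 0.5 × 0.512) = 7.4% at m = 5%.
- k = 4: 10% × (1 − 0.5 × 0.039) = 9.8% at m = 1%, and 10% × (1 − 0.5 × 0.185) = 9.1% at m = 5%.

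Two groups with the same true prevalence would be reported differently because they have different numbers of scheduled samples.

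**The case against.** **The correct figure can be found elsewhere.** Section 9.3.2 also plans antibody status by visit, and Baseline is a sampled visit. Category 6 is one of the tabulated categories, so a reader could add it back. This stands and limits the harm. Immunogenicity is among the other objectives in section 2.1.3, and no hypothesis test depends on Category 8. It does not remove the contradiction: the row labelled as Baseline prevalence would still be wrong, and could disagree with the by-visit table.

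**The bias may be nil.** This also stands. A reader might infer that the prevalence will be too low and will differ between sequences and data cuts. The SAP supports only that it can. If no Baseline-positive subject is in Category 6 or unclassified, the sum is correct.

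**The illustrative percentages can be over-read.** A reader might take 13% to 51% as the understatement of prevalence. It is not. The percentages apply only to Baseline-positive subjects whose observed samples are all negative, a subset of unknown size. They rest on missing rates and independence that the SAP does not supply, and the 14-sample figures do not apply to subjects switched from secukinumab.

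**Early leavers.** A reader might also infer that early withdrawals, subjects who do not enter the OLE, and subjects who go straight into OLE2 without an SFU sample necessarily swell Category 6. The SAP does not say whether a visit that was no longer due counts as missing, and section 3.3 maps early-withdrawal antibody samples to the next scheduled antibody visit. These groups may add to the problem, but the text does not settle it.

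**The falling-titer gap depends on the reading.** Less than a 2.07-fold difference could mean a post-to-Baseline ratio below 2.07, which would cover falls. The reference to the same magnitude favours the two-sided reading but does not settle it.

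**Conclusion.** The contradiction between description and formula is real and appears in two places. The formula can only equal or understate the quantity it names. It omits all of Category 6, Baseline-positive subjects with no post-treatment result and, on the two-sided reading of Category 4, those whose positive titers fall by more than 2.07-fold.

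The size of the understatement cannot be derived from the SAP. The shares in the working show only that small per-sample missing rates could matter over a long sampling schedule. They depend on the assumed rates, on independence between visits, and on how many Baseline-positive subjects are negative afterwards. This is a descriptive immunogenicity output that should be corrected; no efficacy conclusion is affected.

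**What to change.** In both places in section 9.3.2 (the Category 8 definition and the Analysis bullet), define Category 8 as a direct count of all subjects whose Baseline ADAb status is positive, regardless of post-treatment samples, and delete the sum of Categories 3, 4 and 5.

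Base that status on the section's own sample rules, under which a positive screen with no confirmatory result is treated as positive. Wording that required a confirmed positive sample would drop those subjects and bring back an undercount. Replacing the sum with 3+4+5+6 would not be enough either, because subjects with no post-treatment result would still be missed.

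Separately, state which category holds Baseline-positive subjects whose post-treatment titers fall by more than 2.07-fold. Widening Category 4 is one option, but it would label a falling titer as unaffected and change that category's count, so the choice should be deliberate.

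The cost is a change of wording in two places, one simpler derivation and one clarifying sentence. No new data are needed. The reported Baseline prevalence stays the same or rises.
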